#### **IV. Subject Enrollment**

This is a proof of concept, single center study for the donation of HCV-positive hearts to HCV-negative recipients, with preemptive treatment to prevent HCV transmission upon transplantation.

Any patient interested in learning about HCV infection and this study will be invited to voluntarily attend a one-on-one information session where they will be provided information on HCV including treatment options and its current role in cardiac transplantation. Patients will have the opportunity to ask questions throughout this meeting. After the session patients will be given the informed consent information to review at home. If interested they will subsequently return for a screening visit.

A study clinician investigator (licensed physician) will obtain informed consent. The consent form and protocol will be reviewed with the potential subject and any questions will be answered. The subject may be seen in a private area located in the Cardiology Clinic. Subjects will again have the option to take the consent form home with them for at least 24 hours to decide whether or not they wish to participate.

Ability to provide informed consent will be determined by the study investigator in discussion with the subjects treating physician. Subjects who cannot provide informed consent due to their clinical presentation will not be included. Surrogate consent will not be allowed in this study.

## V. Study Procedures

Prior to enrollment in the study, research staff will be working with patient insurance to confirm that the patient insurer will be covering the cost of HCV treatment. In the event that insurance does not agree to cover the cost of HCV DAA therapy, the cost of medication will be covered by pre-established hospital funds.

Patients will initially sign informed consent to be “waitlisted” for HCV-positive donor hearts under this protocol. At the time a heart transplant becomes available, the “waitlisted” patients will be contacted and again sign informed consent for transplantation (standard of care).

Upon receiving notification that an HCV-antibody (Ab) positive donor organ is available, we will review if the organ is nucleic acid testing (NAT) positive or negative. A pre-emptive treatment approach will be used in patients receiving NAT-positive donor organs, and a reactive treatment approach will be performed in patients receiving NAT-negative donor organs, as outlined below:

**A study patient who receives an HCV NAT-negative donor heart (or heart and kidney)** will be followed with HCV viral load (VL) testing per study protocol (on study days 1, 3, 7, 14, 28, 56, 84, 112, 140, 224, 280, and 365)

- If the study patient does not develop a positive VL during this 365 day duration they will not undergo treatment with DAA therapy.
- If the study patient does demonstrate seroconversion *with a positive HCV VL* then we will initiate pan-genotypic therapy per study protocol. A patient’s case will be reviewed and DAA selection made based on individual patient factors with plans to complete a DAA course and monitor for SVR at 12 weeks post-therapy completion.

Upon receiving notification that an HCV-positive donor organ is available with plans for transplantation, a patient’s case will be reviewed and the appropriate DAA selected based on individual patient factors including current labs, medications, and anticipated future post-transplant therapies for any interactions that would preclude safe administration of DAA. **A study patient who receives an HCV NAT-positive donor heart (or heart and kidney)** will be scheduled to receive preemptive treatment with one of the following pan-genotypic DAAs:

- co-formulated sofosbuvir (400 mg)/velapatasvir (100 mg) (EpclusaTM) given orally for a duration of 8 weeks post-transplantation.

OR

- co-formulated glecaprevir (300mg)/pibrentasvir (120mg) (MavyretTM) given orally for a duration of 8 weeks post-transplantation.

*In summary:* Patients who receive HCV NAT-negative organs are monitored with HCV VL testing as per usual protocol. HCV treatment is only initiated in patients who seroconvert *and* become NAT-positive.

Targeted physical assessment, vital sign measurements, emergence of adverse events and concomitant medication usage will be assessed at scheduled visits and as needed at the time of any unscheduled contact during the 56 day study period and/or the 365 day post-dosing safety follow-up.

Study visits post-cardiac transplantation will occur on days 0, 1, 3, 7, 14, 28, 42, 56, 70, 84, 112, 140, 224, 280, 365.

Version Date: 7/3/2019

The **screening visit** will take place within an estimated 1-5 months prior to cardiac transplantation. When enrollment is complete the patient's insurer will be contacted to confirm coverage of a pan-genotypic DAA. **Day 0** of this study represents the day of cardiac transplantation, initiation of study drug will begin within 7 days of transplantation. After initiation of therapy, each subject will receive their study drug daily through course completion.

Pre-screening workup

Informed consent for evaluation

Completed education session with RN and MD/NP

Complete medical history

Complete physical exam

Laboratory screening (HCV Ab and VL, HIV, CMP, CBC with differential, Coagulation tests)

ECG monitoring

Quality of life assessment (SF-36)

Baseline testing (day of transplant, day 0)

HCV RNA, CMP, LFTs, CBC with differential, Coagulation tests

Review of concomitant meds

Week 1 (Visits on Day 3, 7)

HCV RNA, CMP, LFTs, CBC with differential

Adverse event reporting

Standard of care post-transplant visit

ECG monitoring

Review of concomitant meds

Week 2 (Day 14)

HCV RNA, CMP, LFTs, CBC with differential

Adverse event reporting

Standard of care post-transplant visit

Review of concomitant meds

Week 4 (Day 28)

HCV RNA, HCV Ab, CMP, LFTs, CBC with differential

Adverse event reporting

Standard of care post-transplant visit

Review of concomitant meds

Week 6 (Day 42)

HCV RNA, CMP, LFTs, CBC with differential

Adverse event reporting

Standard of care post-transplant visit

Review of concomitant meds

Week 8 (Day 56)

HCV RNA, CMP, LFTs, CBC with differential

Adverse event reporting

Standard of care post-transplant visit

Review of concomitant meds

Quality of life assessment (SF-36)

Week 9, (Day 63); One week post DAA completion

Tacrolimus level (for patients on Mavyret)

Week 10, SVR 2 (Day 70)

HCV RNA, HCV Ab, CMP, LFTs, CBC with differential

Tacrolimus level

Adverse event reporting

Standard of care post-transplant visit

Review of concomitant meds

Week 12, SVR 4 (Day 84)

HCV RNA, CMP, LFTs, CBC with differential

Adverse event reporting

Standard of care post-transplant visit

Review of concomitant meds

Week 16, SVR 8 (Day 112)

HCV RNA, CMP, LFTs, CBC with differential

Adverse event reporting

Standard of care post-transplant visit

Review of concomitant meds

Week 20, SVR 12 Visit (Day 140)

HCV RNA, CMP, LFTs, CBC with differential

Review of concomitant meds

Quality of life assessments (SF-36)

Week 32, SVR 24 Visit (Day 224)

HCV RNA, CMP, LFTs, CBC with differential

Review of concomitant meds

1 year visit (Day 365)

HCV RNA, CMP, LFTs, CBC with differential

Review of concomitant meds

Quality of Life assessment (SF-36)

**Serum pregnancy tests** (for all females of childbearing potential) will be conducted at screening and performed immediately prior to transplantation for all women of reproductive age as a standard of care. Because the effect, if any, of Epclusa™ or Mavyret™ on an embryo or fetus (developing baby still in the womb) is not known, patients may not participate in this study if they are pregnant, breastfeeding, or planning to become pregnant. Females who are able to become pregnant must agree to use adequate birth control use throughout the duration of the study. For the purposes of this study, adequate birth control means one of the following:

1. Intrauterine device (IUD)
2. Condom with spermicide
3. Diaphragm with spermicide
4. Complete abstinence (not having sex at all)

Hormonal forms of birth control including birth control pills, vaginal rings (like NuvaRing), implants (like Implanon), or injections (like Depo-Provera) may not work during treatment with Epclusa™ or

Version Date: 7/3/2019

Mavyret™ and are not on the acceptable forms of birth control list. After patients have been off Epclusa™ or Mavyret™ for at least two weeks, they can again begin to use a hormonal form of birth control.

**Men** enrolled in the protocol must also agree to use adequate contraception while participating in this study. Adequate contraception is:

1. Condom with spermicide, and
2. Female partners must use an approved method of birth control as listed above

Men must also agree that they will not donate sperm during the entire study period.

**Donor genotyping** – HCV genotyping will be performed by the MGH Core Lab. Because the treatment in this study is pan-genotypic, we do not need genotype results to return prior to medication administration; delays in HCV genotyping will not influence initiation of the study drug.

**Achievement of Sustained Virologic Response (SVR).** Patients who received an **HCV NAT-positive** donor heart who have an undetectable viral load 12 weeks after completing therapy (SVR 12) are patients in whom the use of DAA has successfully prevented HCV infection transmission. If during monitoring for these patients a positive viral load is detected and at the end of their 8 week therapy course, a plan will be made to extend the patient's course of Epclusa™ or Mavyret™ from 8 weeks to 12 weeks. We may also add additional Hep C medications to increase the chance of curing the Hep C infection. If this happens, we will plan to review all of these details in person with the patient and determine, based on recent updates and clinical practice, the best regimen with which to treat the patient and achieve HCV cure.

This study has received IND exemption from the FDA regarding use of pan-genotypic DAA therapy; a letter has been posted on the Attachments tab in Insight to provide documentation.

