## **VI. Biostatistical Analysis**

### Variables/Time Points of Interest

The primary variable of interest will be HCV RNA at the multiple time-points assessed during and after treatment.

The primary efficacy outcome “Prevention of HCV Transmission” will be determined by a negative HCV RNA test.

The safety outcomes include summation of treatment related adverse events and transplant rejection or patient mortality. On treatment eGFR, proteinuria, hemoglobin, and liver function tests will be summarized to assess safety.

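### Every SVR12 is counted as prevented transmission, even after viremia, so the SVR12 rate alone cannot answer Aim 1; secondarily, the SVR12 visit is timed from transplant rather than from last dose

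*Combined protocol and SAP*

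**What the plan says.** **The label.** Aim 1 (section II) is to determine whether preemptive therapy prevents transmission from an HCV-positive heart to an HCV-negative recipient. The SVR paragraph of section V states that recipients of NAT-positive hearts with an "undetectable viral load 12 weeks after completing therapy (SVR 12) are patients in whom the use of DAA has successfully prevented HCV infection transmission". It sets no condition on earlier viremia. The same paragraph plans for recipients with a positive viral load: the course may be lengthened "from 8 weeks to 12 weeks", and "We may also add additional Hep C medications to increase the chance of curing the Hep C infection". In section VI, the primary outcome carries the name of prevention and "will be determined by a negative HCV RNA test"; Statistical Methods then reports the SVR12 rate with an exact 95% CI. Aim 3 reports the proportion with undetectable RNA at nine study days, starting at Day 7.

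**The calendar.** Day 0 is the day of transplant. In section V, "initiation of study drug will begin within 7 days of transplantation", after which "each subject will receive their study drug daily through course completion". Visits are fixed days after transplant and no windows are given. The schedule has "Week 9, (Day 63); One week post DAA completion" and labels Day 140 as SVR 12 and Day 224 as SVR 24.

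**The concern.** A recipient who never has detectable RNA and a recipient who becomes infected and is then cured are clinically different results. Only the first shows that transmission was prevented. The plan gives both the same label and reports them in one rate, so a high SVR12 rate could be read as showing that early dosing stops infection when part of it shows that donor-derived infection can be treated. With drug starting anywhere from just before the operating room (section VII, Study Drug Exposure) to Day 7, the cohort may contain both.

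The timing question concerns the same endpoint. SVR12 is defined from the end of therapy, but its draw sits on a calendar that counts from transplant. If the two diverge, the scheduled sample does not meet the plan's own definition. The recipients most affected are those given a longer course because they were viremic.

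**Working it through.** **1. Apply the success rule to three recipients of NAT-positive hearts (hypothetical cases).**

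- A: no positive RNA at any visit; undetectable 12 weeks after therapy.
- B: positive RNA on Day 7, cleared on treatment; undetectable 12 weeks after therapy.
- C: positive at the end of 8 weeks, extended to 12 weeks with an added drug, cleared; undetectable 12 weeks after therapy.

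Under the SVR paragraph of section V, all three count as prevented transmission. Only A matches Aim 1 as worded.

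**2. Can Aim 3 separate them?** It gives one proportion per visit. Suppose 45 of 50 are undetectable on Day 7 and 45 of 50 on Day 14. If the same 5 people are positive both times, 5 were ever viremic; if they are different people, 5 + 5 = 10 were. The per-visit figures fit either. Aim 3 also leaves out Days 0, 3, 42 and 70, when section V draws RNA.

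**3. Size of the label effect.** Let v be the number ever viremic among 50 recipients who all reach SVR12. The documents do not give v, so the values are assumptions. The never-viremic share is (50 − v)/50, with exact (Clopper-Pearson) 95% CI.

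| v (assumed) | Never viremic | Exact 95% CI |
|---|---|---|
| 0 | 50/50 = 100% | 92.9 to 100 |
| 5 | 45/50 = 90% | 78.2 to 96.7 |
| 10 | 40/50 = 80% | 66.3 to 90.0 |
| 25 | 25/50 = 50% | 35.5 to 64.5 |

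In every row the plan would report 50/50.

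**4. Reproduce the calendar.** With completion on Day 56: 56 + 7 = 63, 56 + 14 = 70, 56 + 28 = 84, 56 + 56 = 112, 56 + 84 = 140, 56 + 168 = 224. Every labelled day is recovered, so the schedule assumes completion about Day 56.

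**5. Move the start day.** For first dose on Day s and 56 daily doses, last dose = s + 55; days off drug at Day 140 = 140 − (s + 55) = 85 − s; earliest day that is 84 days after last dose = s + 55 + 84 = 139 + s.

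| First dose (s) | Last dose | Days off drug at Day 140 | Weeks | Earliest SVR12 day |
|---|---|---|---|---|
| 0 | 55 | 85 | 12.1 | 139 |
| 1 | 56 | 84 | 12.0 | 140 |
| 3 | 58 | 82 | 11.7 | 142 |
| 5 | 60 | 80 | 11.4 | 144 |
| 7 | 62 | 78 | 11.1 | 146 |

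If completion is taken as the day after the last dose (s + 56), the Day 7 row becomes 77 days and Day 147. The Day 7 shortfall is thus 84 − 78 = 6 or 84 − 77 = 7 days.

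**6. Extended course, 84 doses without a break.** Last dose = s + 83; days off drug at Day 140 = 57 − s, which is 57 (s = 0) to 50 (s = 7). The shortfall is 84 − 57 = 27 to 84 − 50 = 34 days, or 28 to 35 days counted from completion. The true SVR12 day is 167 + s = 167 to 174 (168 to 175 from completion). After Day 140 the next scheduled RNA is Day 224, which is 141 to 134 days after the last dose.

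**The case against.** The best defence of the label is that SVR12 is the statistic actually named in Statistical Methods, that the Background hypothesis speaks of preventing or eliminating infection, and that Aim 3 will show viremia by visit next to the SVR12 rate. Whether one brief positive RNA amounts to transmission is also partly a matter of definition. This softens the point but does not remove it: Aim 1 and the primary outcome are named prevention alone, the success rule applies that name to everyone with SVR12, and Aim 3 gives no ever-viremic count.

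On timing, the defence is stronger. SVR12 is defined from the end of treatment in Hypothesis 1 and in section V, Day 7 is an outer limit, no document says how many will start late, and later RNA on Days 224 and 365 gives confirmation. For 8-week courses this is a visit-window clarification. For an extended course, individual planning is foreseen, but no draw is scheduled near the right date.

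A reader might go further in four ways that the documents do not support:

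- *The primary outcome has no time point.* Its sentence in section VI has none, but Hypothesis 1, the SVR paragraph and Statistical Methods together set it at 12 weeks after treatment.
- *A Day 7 starter stops at Day 56 and receives only 49 or 50 doses.* The course is worded as 8 weeks post-transplantation, but section V also requires daily drug to course completion and refers to an 8-week course. A full course is the better reading.
- *Late starts distort the SVR12 rate.* A shortfall of at most a week gives no basis for that.
- *Prevention will turn out to be 50 to 90%.* Those figures rest on assumed v, and 50 recipients is a ceiling.

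**Conclusion.** The concern holds, mainly for the label. As written, the SVR12 rate is a valid summary of virologic outcome but cannot say how often transmission was prevented, because it pools never-viremic recipients with those viremic and then cured. The size of the gap equals the share ever viremic among those with SVR12, which the documents do not give. SVR12 itself is not in question.

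The timing point is secondary. For an 8-week course the Day 140 draw is at most 6 to 7 days early, probably with little effect on the rate. For a 12-week course it is 4 to 5 weeks early and does not meet the SVR12 definition. This assumes daily dosing, a full course, visits on their nominal days and, for the longer course, no break. This is a single-arm pilot with no decision threshold, so the change is worth making for correct interpretation; it does not threaten the study.

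**What to change.** **Label.** Keep the SVR12 rate and exact CI as planned. Add a descriptive split of all treated recipients of NAT-positive hearts, using RNA already drawn, in which each person falls in exactly one group:

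- (a) SVR12 and no positive RNA at any time after transplant: prevention.
- (b) SVR12 after any positive RNA: cure. Subdivide by first positive at or before first dose versus after it, and flag any extended or intensified course.
- (c) No SVR12: virologic failure, death or missing, shown separately.

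Give an exact CI for (a). Report start day beside the table, since a later start leaves more time for pre-dose viremia. Do not describe (b) as prevented transmission.

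**Timing.** State that the 8 weeks run from first dose. Record first- and last-dose dates, and the time of first dose relative to that day's RNA sample; in a Day 7 starter, draw before dosing. Take the SVR12 sample at least 84 days after last dose. A window of about +7 days on Day 140 covers 8-week courses, and the same draw can serve Aim 3. Add one SVR12 draw after an extended course.

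**Cost.** Protocol wording, dose dates on the case report form if not already there, one table, and one extra draw per extended course. Late starters are seen up to a week later. The groups will be small, and a pre-dose RNA may be a few days old. The strict rule also means that a brief early positive RNA does not count as prevention; the subdivision of (b) lets readers see how often that happens.

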### Statistical Methods

Patient characteristics for this cohort (N=50 receiving HCV+ organ) will be presented with summary statistics for baseline demographics and clinical variables. The SVR12 rate will be presented and 95% CI constructed with the exact test. Mean and standard deviation for on-treatment laboratory values will be presented to analyze safety.

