## **Risks Related to Study Procedures**

Risks of Blood Draws

The patient may have a bruise (a black-and-blue mark) or pain where researchers take the blood samples. There is also a small risk of feeling lightheaded, fainting, or infection. A total of up to 53 tablespoons of blood will be drawn over the course of the entire study.

Risks to an Embryo or Fetus, or to a Breastfeeding Infant

Because the effect, if any, of EpclusaTM or MavyretTM on an embryo or fetus is not known, the patient may not participate in this study if they are pregnant, breastfeeding, or planning to become pregnant. This is not a new requirement necessitated by this protocol, as patients on the cardiac transplant list must also agree to not become pregnant while awaiting and for a period of time after transplantation.

Study Drug Exposure

Patients will not receive the study drug until post-transplant or just prior to their transport to the operating room (OR) to receive a donor organ. We anticipate that the likelihood of a patient not receiving an organ after taking a dose of study drug is extremely low. However, in the event that a patient does receive the initial dose of study drug and not an HCV-positive heart, we would then plan to immediately stop the study drug. No additional study drug would be given unless the patient was again offered an HCV-positive organ and returning to the OR.

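### Laboratory safety is planned only as the mean and SD of on-treatment values, so the Day 0 draw is never used to show within-patient change

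*Combined protocol and SAP*

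**What the plan says.** Section VI, under Variables/Time Points of Interest, names the laboratory safety variables: "On treatment eGFR, proteinuria, hemoglobin, and liver function tests will be summarized to assess safety". Under Statistical Methods it gives the whole analysis: "Mean and standard deviation for on-treatment laboratory values will be presented to analyze safety". No change score, shift table, reference value or rule for patients who die or leave is stated.

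The same section says that patient characteristics "will be presented with summary statistics for baseline demographics and clinical variables". That is a separate group summary. It names no laboratory test and is not linked to the on-treatment values.

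The data for a change score are collected. Section V heads one visit "Baseline testing (day of transplant, day 0" and lists "HCV RNA, CMP, LFTs, CBC with differential, Coagulation tests" for it. Chemistry, liver tests and blood count recur at Days 3, 7, 14, 28, 42 and 56. A screening panel, an estimated 1 to 5 months before transplant, also includes chemistry and blood count: "Laboratory screening (HCV Ab and VL, HIV, CMP, CBC with differential, Coagulation tests".

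Two statements fix when dosing starts relative to Day 0. Section V says "initiation of study drug will begin within 7 days of transplantation". Section VII, under Risks Related to Study Procedures, says "Patients will not receive the study drug until post-transplant or just prior to their transport to the operating room (OR".

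**The concern.** Aim 2 is safety and tolerability. There is one treated cohort of up to 50 patients and no control arm, so the patient's own earlier value is the only internal reference for eGFR, hemoglobin and liver tests. A mean eGFR at Day 28 with its SD describes the level at Day 28. It does not say whether anyone got worse, by how much, or how many did.

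The recipients are also mixed. Listing status 1A, 1B and 2 are all mentioned in Section III, and candidates for simultaneous heart-kidney transplant are eligible. The kidney graft itself changes renal function. One cohort mean can combine falls in some patients with rises in others. What is at stake is whether the laboratory results can support a statement about change under Aim 2.

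**Working it through.** The plan gives no precision or power figure for laboratory safety, so there is none to reproduce. The inputs from the documents are up to 50 treated patients, the visit schedule and the planned summaries. The SD, correlation, losses and number of heart-kidney recipients below are assumptions, because the documents give none of them. eGFR is assumed to be computed from the chemistry panel.

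**1. What visit means can show.** If all patients have both values, mean(later) − mean(Day 0) = mean(later − Day 0). Case mix therefore does not bias the mean change. The spread of change is a different matter: with a common SD s and correlation r between visits, SD of change = s√(2(1 − r)). For s = 20 this is 20√1.4 = 23.7 at r = 0.3 and 20√0.2 = 8.9 at r = 0.9. The visit SDs are 20 in both cases, so they cannot tell the two apart.

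**2. Precision (n = 50, s = 20).**
- Unpaired 95% half-width: 1.96 × 20 × √(2/50) = 7.8.
- Paired 95% half-width: 1.96 × 20 × √(2(1 − r)/50).

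| r | Paired | Unpaired |
|---|---|---|
| 0.3 | 6.6 | 7.8 |
| 0.5 | 5.5 | 7.8 |
| 0.7 | 4.3 | 7.8 |
| 0.9 | 2.5 | 7.8 |

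Major surgery lies between Day 0 and later values, so the lower correlations must be considered.

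**3. Subgroups.** Suppose 45 heart-only recipients fall by 8 from 65 to 57, and 5 heart-kidney recipients go from 20 to 60. The Day 0 mean is (5 × 20 + 45 × 65)/50 = 60.5. The later mean is (5 × 60 + 45 × 57)/50 = 57.3. The difference is −3.2, and the mean within-patient change is also −3.2. Pairing alone does not reveal the fall of 8; a split or a display of individual changes does.

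**4. Selective loss.** Simulation with 50 patients, SD 20 and a true change of −5. Five patients are lost, with weight exp(−z), where z is the standardised quantity that drives loss; 20,000 runs. Unpaired is the later mean of those remaining minus the Day 0 mean of all 50. Paired is the mean change in those with both values.

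| Loss depends on | r | Unpaired | Paired |
|---|---|---|---|
| Low Day 0 value | 0.8 | −3.5 | −5.4 |
| Low on-treatment value | 0.8 | −3.1 | −4.6 |
| Largest decline | 0.8 | −4.4 | −3.8 |
| Low Day 0 value | 0.5 | −4.0 | −6.0 |
| Largest decline | 0.5 | −4.0 | −3.1 |

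Both summaries are biased. Paired change is closer to −5 in the first two rows, about equally far off in the fourth (in the direction of overstating the fall), and further off when the patients who decline most are the ones who leave.

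**5. Reference value.** The two statements on first dose allow it just before the operating room or up to 7 days after transplant. The last pre-dose draw is then pre-operative for some patients and post-operative for others, and a Day 3 draw may itself be pre-dose. Change from that value alone would pool different quantities, so change from Day 0 is needed beside it.

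**The case against.** The strongest reply is that this is a descriptive pilot and laboratory means are not its only safety evidence. Section VI also lists treatment-related adverse events, rejection and mortality. Adverse events are recorded at the on-treatment visits, and Section IX provides a safety review every three months. A marked decline in one patient could surface there. The wording under Variables/Time Points of Interest does not forbid change scores, and the plan proposes no unpaired test, so 7.8 is not a planned result. All of this stands, and it keeps the priority low. It does not supply the missing analysis: a modest fall across the cohort need not be reported as an adverse event, and the analysis sentence names only on-treatment levels.

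A reader might infer more: that the planned means would mask a real drug-period decline, because of case mix and because the sickest leave, and that pairing would uncover it. The documents do not support that. Case mix does not bias the mean with complete data. The documents give no mortality, loss or laboratory SD from which to size a survivor effect. The direction of bias depends on why patients leave, and complete-case pairing can be the worse summary. Nor can change from Day 0 isolate the drug, since surgery and immunosuppression fall in the same interval and there is no control arm.

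**Conclusion.** The gap is real but small. The stated analysis cannot show laboratory change for Aim 2, although chemistry, liver tests and blood count are collected at a visit the protocol itself calls baseline. Adding paired change would give the size and spread of change, let individual and subgroup changes be seen, and narrow the 95% half-width from 7.8 to between 6.6 and 2.5. That range rests on an assumed SD of 20, 50 complete pairs and correlations from 0.3 to 0.9. No claim is made that the planned means would hide a decline of any particular size. Priority: minor. The primary SVR12 analysis is unaffected.

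**What to change.** Add to Section VI, Statistical Methods:

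> For eGFR, hemoglobin and liver tests, report at each on-treatment visit the within-patient change from Day 0 and, where it differs, from the last value before the first DAA dose, as mean, SD and 95% CI with individual changes displayed, in patients with both values. Give the number contributing and the numbers who died or left, show heart-only and heart-kidney recipients separately, and show the baseline mean for the same patients.

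Keep the planned level means. State that change includes the effects of surgery and immunosuppression, is not attributed to the DAA alone, and that complete-case pairing does not remove survivor bias.

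Proteinuria is left out of this text because no urine protein test appears in the listed visits, so its change could not be computed from the schedule as written.

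The cost is a short addition to Section VI and one extra table that must carry the caveat. No new samples or visits are needed.

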#### ***Aim 3***

Determine the proportion of subjects with undetectable serum HCV RNA at study day 7, 14, 28, 56, 84, 112, 140, 224, and 365 in cardiac transplant recipients receiving pan-genotypic DAA therapy following transplant from an HCV infected donor

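### SVR12 is defined from the end of therapy but sampled at a fixed Day 140 after transplant; for a course extended to 12 weeks that is only 7.0 to 8.0 weeks off drug, and no visit falls at the true 12-week point

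*Combined protocol and SAP*

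**What the plan says.** **Definition.** Section V (Achievement of Sustained Virologic Response) treats HCV transmission as prevented when a recipient of a NAT-positive heart has "undetectable viral load 12 weeks after completing therapy (SVR 12". Hypothesis 1 in Section II also counts the 12 weeks from the end of treatment.

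**Schedule.** The visit list in Section V counts from transplant as Day 0: "Study visits post-cardiac transplantation will occur on days 0, 1, 3, 7, 14, 28, 42, 56, 70, 84, 112, 140, 224, 280, 365". The SVR labels are attached to those fixed days, from "Week 10, SVR 2 (Day 70" through "Week 20, SVR 12 Visit (Day 140" to the SVR 24 visit on Day 224. Aim 3 likewise lists "undetectable serum HCV RNA at study day 7, 14, 28, 56, 84, 112, 140, 224, and 365". Both lists go from Day 140 straight to Day 224.

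**Course length.** The planned course is 8 weeks, and dosing may start up to 7 days after transplant. Section V then provides for a longer course: "If during monitoring for these patients a positive viral load is detected and at the end of their 8 week therapy course", treatment is to be lengthened "from 8 weeks to 12 weeks". It continues: "We may also add additional Hep C medications".

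**Analysis.** Section VI (Statistical Methods) reports the SVR12 rate with an exact 95% CI and names no other efficacy analysis. It does not say which sample supplies SVR12 after an extended course, or whether clearance after an extended or augmented course counts as prevention. No visit window is given anywhere.

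**The concern.** The endpoint and its visit have different time origins: end of therapy for one, transplant for the other. They coincide for the planned course, but the protocol itself provides for a course that ends four weeks later and leaves the SVR visits where they were. A team following the written schedule would record as SVR12 a sample that does not meet the protocol's definition, and would take no sample at the time that does.

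Extension follows a positive viral load, so the affected patients bear most directly on whether transmission was prevented. In an open-label, single-arm study of up to 50 treated patients, leaving the rule unstated also means it could be chosen after their results are known.

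**Working it through.** **Inputs (Section V unless stated)**
- Start day *s*: 0 to 7. Dosing begins within 7 days of transplant. Section VII (Study Drug Exposure) also allows a first dose shortly before surgery, which fits *s* = 0.
- Course length *d*: 56 days as planned, 84 days if extended. The extension is assumed to follow without a gap.
- End of treatment = *s* + *d*. This is the schedule's own convention: it labels Day 63 as one week after completion, so an 8-week course from Day 0 ends on Day 56.
- SVR12 interval: 12 × 7 = 84 days.

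**Formulas**
- Days off drug at visit day *V* = *V* − (*s* + *d*)
- True SVR12 day = *s* + *d* + 84

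**Reproducing the plan's figure.** With *s* = 0 and *d* = 56, the SVR12 day is 0 + 56 + 84 = 140, as stated. Days 70, 84, 112, 140 and 224 are then 14, 28, 56, 84 and 168 days off drug, which is 2, 4, 8, 12 and 24 weeks. All five SVR labels are right for that course.

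**Applying the formulas to the other permitted courses (days off drug)**

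| Course | End | SVR 2 (Day 70) | SVR 4 (Day 84) | SVR 8 (Day 112) | SVR 12 (Day 140) | SVR 24 (Day 224) | True SVR12 day |
|---|---|---|---|---|---|---|---|
| 8 wk, start Day 0 | 56 | 14 | 28 | 56 | 84 | 168 | 140 |
| 8 wk, start Day 7 | 63 | 7 | 21 | 49 | 77 | 161 | 147 |
| 12 wk, start Day 0 | 84 | −14 | 0 | 28 | 56 | 140 | 168 |
| 12 wk, start Day 7 | 91 | −21 | −7 | 21 | 49 | 133 | 175 |

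For an extended course:
- The SVR 2 visit falls on treatment, and the SVR 4 visit falls at or before its end.
- Day 140 is 49/7 = 7.0 to 56/7 = 8.0 weeks off drug, which is 84 − 56 = 28 to 84 − 49 = 35 days short.
- The 12-week point is Day 168 to 175, where no visit is listed.
- The next RNA sample, Day 224, is 133/7 = 19.0 to 140/7 = 20.0 weeks off drug. Day 365 is 365 − 91 = 274 to 365 − 84 = 281 days off drug.

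**Other readings**
- If courses are counted from transplant whatever the first-dose day, an extended course ends on Day 84. Day 140 is then 56 days off drug (28 short), and the 12-week point is Day 168.
- If the last dose falls on day *s* + *d* − 1, each off-drug figure rises by one day: 50 to 57 days at Day 140 for an extended course.
- An assumed 7-day gap before the extension lowers Day 140 to 42 to 49 days off drug.
- For an unextended course, Day 140 is at most 7 days early.

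No reading brings Day 140 to 84 days for an extended course.

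**Classification of extended patients (a separate question).** If all 50 are treated, each patient cleared only after an extended or augmented course carries 1/50 = 2 percentage points, and more if fewer are treated. As an illustration, 50/50 has an exact 95% lower limit of 0.025^(1/50) = 92.9%. For 49/50 the exact lower limit is 89.4%, so one reclassified patient lowers it by 92.9 − 89.4 = 3.5 points. The documents give no extension rate, so no total shift can be claimed.

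**The case against.** The strongest reply is that the definition governs and the day labels only describe the planned course. The definition is not limited to 8 weeks. For NAT-negative recipients who are treated later, Section V asks for SVR at 12 weeks after completion and names no day. On that reading a Day 140 sample from an extended patient is simply not SVR12. The endpoint is then sound and only a visit for a contingency is missing.

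The effect may also be small:
- Timing changes a result only if RNA is undetectable at 7 to 8 weeks off drug and detectable at 12. The documents give no figure for this, and the later samples would show viraemia.
- If extended patients count as failures of prevention, their Day 140 sample cannot move the rate.
- Section I cites cure rates of 98 to 100% outside transplantation. If non-cure is taken as a rough ceiling for extension, which is an assumption, at most 2% × 50 = 1 patient is expected. A broader reading of the extension trigger could give more.
- The study is a pilot with no success threshold.
- The 7.0-week and Day 175 ends require a Day 7 start with a full course counted from the first dose.

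The points on size and range stand, and they limit the weight of the finding. The first point does not remove it: even if the definition governs, no sample is scheduled at the defined time and no rule says what replaces it.

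**Conclusion.** The concern holds: for extended courses the schedule is wrong as written and should be fixed. Day 140 is 28 to 35 days too early for SVR12, and the 12-week point (Day 168 to 175) falls between scheduled visits. The range assumes a continuous 12-week course started on Day 0 to 7. If every course is counted from transplant, only the 28-day shortfall and Day 168 remain.

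The loss is in timing and labelling, because Day 224 and Day 365 RNA would still detect later viraemia. Only extended patients are affected, in a number the documents do not allow one to estimate reliably. The early Day 140 sample in unextended courses, by at most 7 days, is minor. The 2 points per patient belongs to the unstated classification rule, not to the timing error.

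**What to change.** 1. Time the SVR visits from each patient's actual last dose. Take SVR12 at last dose + 84 days with a stated window.
   - One example is 77 to 98 days. This is a suggestion and has no source in the documents. It accepts every Day 140 sample from an unextended course (77 to 84 days).
   - For a continuous extended course that window is Day 84 + 77 = 161 to 84 + 98 = 182 (Day 0 start), or Day 91 + 77 = 168 to 91 + 98 = 189 (Day 7 start).
   - State that a Day 140 sample from an extended course is not SVR12.
2. As a cheaper alternative, pre-specify that the Day 224 sample decides the outcome for extended courses, and say how death or loss before Day 224 is handled.
3. In Section VI, state whether patients cleared only after an extended or augmented course count as prevention successes. Report the rate under the opposite rule, with its exact CI, as a sensitivity analysis.
4. Reconcile the passages that count the course from transplant, the 7-day start window, the Day 63 label and the sentence that triggers extension, which can be read in more than one way. No view is taken here on treatment duration or on when to extend.

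The cost is protocol wording and one analysis rule, with no extra patients. Each extended patient needs one moved or added blood draw, or none if Day 224 is designated. With the example window nothing changes for unextended patients.
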